30 to classical methods. In SIRIUS we will prospectively challenge this hypothesis to address the
31 question of how often a better or final diagnosis can be delivered by WGS and/or WTS and if
32 unclear cases can be efficiently resolved.

33

34 **Type of Research:** observational study, diagnostic study, hematology, leukemia, next
35 generation sequencing

36

37 **Intervention:** none

38 **APPROVAL**

39 This study will be conducted with the utmost respect for individual patients in accordance with
40 the requirements of this diagnostic trial protocol and especially in accordance with the
41 following:

42 • Good clinical practice directive (European Union) (2005/28/EC)

43 • The ethical principles in accordance with the Declaration of Helsinki

44 • International Conference on Harmonization (ICH) E6 Good Clinical Practice:
45 consolidated guideline

46 • Guidelines for Good Clinical Practice (*Deutsche Forschungsgemeinschaft DFG*)

47 • Standards and guidelines for the interpretation of sequence variants (PMID: 25741868)

48 • All applicable laws and regulations, including, without limitation, data privacy laws,
49 clinical trial disclosure laws, and regulations.

50 **I. INTRODUCTION**

51 1. Background and Rationale

52 Treatment of hematological diseases relies on a single cardinal prerequisite: correct
53 classification within the broad specter of malignant diseases arising from the hematopoietic
54 system. With the ever-expanding availability of distinct yet complementary diagnostic tools,
55 our understanding of the landscape of hematological diseases steadily increases. As such, the
56 current consensus classification as summarized through the WHO classification (2017)
57 represents a compass guiding diagnostic algorithms to the correct diagnosis. Today, the gold
58 standard of routine diagnostic process relies on five methodological pillars: cytomorphology,
59 histology, chromosomal cytogenetics, immunophenotyping, and molecular genetic testing.
60 This leads to a treatment enabling diagnosis in the vast majority of cases. However,
61 approximately 10 % of cases remain unresolved from a diagnostic point of view and hence do
62 not lead to a satisfactory diagnosis according to current WHO standards (2017). We intend to
63 solve this issue to provide illuminating diagnostic guidance for the best possible patient's care.

64 2. Objectives

65 To address this problem, we hypothesize that novel high throughput sequencing methods, e.g.,

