66 whole genome and/or whole transcriptome sequencing are able – by virtue of painting a more
67 delicate genetic portrait of a tumor sample – to provide a more accurate diagnosis.
68 To this end we generated a reference collection of 5,500 samples with the full spectrum of
69 hematological malignancies, for which we performed whole-genome sequencing as well as
70 whole-transcriptome sequencing. Moreover, gold standard diagnoses according to WHO
71 classification with all needed techniques, all performed in MLL, clinical data and therapy
72 response data are fully available for these cases. The main advantage of this reference

73 collection consists of the unambiguity of each diagnosis, providing a reference framework for
74 any further classification and diagnosis especially in difficult cases.

75 Therefore, SIRIUS will compare the diagnostic superiority of WGS or WTS to the combined
76 approach with gold standard results and by matching the obtained results to the nearest “digital
77 sibling” within our reference cohort of more than 5,500 WGS and WTS (both in 93% of cases).

78 To this end, we will use an inhouse developed matching algorithm, which is able to match
79 genomic or transcriptomic profiles to a group of similar cases and gold standard results from
80 timepoint of this study. Current workflows intended to generate WTS/WGS data from patient
81 samples – all while fulfilling state of the art accreditation (ISO 15189) – require up to 5 – 7
82 days. This is largely comparable to classical methods but holds the promise to replace error
83 prone and arduous iterations in the methodological work up. The objective is to test whether
84 WTS and/or WGS based approaches can surpass classical methods regarding diagnostic
85 precision and routine reliability. Here we will test this hypothesis in a prospective real-world
86 setting under diagnostically difficult circumstances.

87 **II. STUDY DESIGN**

88 1. Type of Study

89 SIRIUS is conducted as a monocentric prospective case-control study. The study population
90 consists of carefully chosen patients with potential hematological malignancy, for which
91 current diagnostic methods were not sufficient to provide clear-cut diagnosis and definitive
92 clinical guidance. SIRIUS is entirely a non-interventional study without therapeutic
93 consequences for direct patient care. Data will be used as research study and micro-cost
94 analysis will be provided.

95 2. Duration of Study

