96 SIRIUS will be conducted for a total number of 110 patients with inconclusive diagnosis by
97 gold standard techniques for a total of up to nine months after the first enrollment. Patients to
98 qualify for study will be selected by referring center and PI before material is send to MLL.

99 3. Quality Control

100 Due to the heterogeneity in quality of blood and bone marrow samples arriving at MLL,
101 SIRIUS is preceded by a rigorous quality assessment of every patient history, data already
102 available and sample source and quality to be potentially included in the present study. The
103 minimal requirements are listed in III.

104 4. Primary Study Endpoints

105 Overall, the efficacy and supremacy of WGS/WTS analysis will be subjected to current
106 standard procedures. The primary endpoint will be assessed as follows: unclear cases will be
107 subjected to three diagnostic algorithms:

108 (1) Inhouse at referring site by histopathological diagnosis in the context of a hematological
109 tumor board according to current standards (“best practice”)

110 (2) Current gold-standard diagnostic workup as performed routinely by the MLL,
111 consisting of

112 a. Cytomorphological diagnosis
113 b. Immunophenotypic diagnosis
114 c. Chromosomal banding analysis
115 d. Molecular testing
116 e. NGS based Targeted panel sequencing

117 (3) WGS and WTS sequencing plus matching to nearest digital sibling in 5,5k cohort

118 The results of (2) and (3) arms will be first compared to the result obtained in (1) since this is
119 the therapy guiding approach *in domo*. Clinical follow-up observations will be made to assess
120 the success of this first diagnosis.

121 Next results from (2) and (3) will be compared against each other to obtain an assessment of
122 replaceability of current gold-standard methods to either WGS or WTS and WGS/WTS
123 combined. If both approaches do not yield a similar conclusion, specific data from (2) will be
124 added to results in (3) until a definitive assessment can be made.

125 5. Secondary Study Endpoints

126 • Turn-over time until potential therapy guiding diagnosis
127 • Cost-effectiveness until timepoint of diagnosis and therapy
128 • Compare WES to WGS data in SIRIUS cohort
129 • Identify number of potential actionable targets for which a therapy has been approved
130 but identification was missed in (1) and (2)
131 • Identify putative disease stage in comparison to (2) and clinical history

132

133

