134 **III. SUBJECT SELECTION AND WITHDRAWAL**

135

136 1. Number Of Subjects

137 SIRIUS intends to enroll a total number of 110 cases provided by approximately 50 certified
138 hematological centers.

139

140 2. Gender, Age

141 Patients' samples from both sexes will be used (male and female). Only samples from adult
142 patients (18 years or older) will be used.

143

144 3. Inclusion Criteria

- 145 • Patients having been investigated with a suspected hematological disorder and:
 - 146 ○ Having unclear diagnosis after internal routine diagnosis
 - 147 ○ Unusual clinical course
 - 148 ○ Unusual r/r status or non-responder
 - 149 ○ Multiple parallel hematological conditions
 - 150 ○ Difficult/rare therapy associated/secondary neoplasms
- 151 • Current diagnostic work-up is not satisfactory in terms of (1) accuracy (2) clinical
152 behavior
- 153 • Only samples of patients min. 18 years of age will be used
- 154 • Material with a minimum of 20% tumor content in bone-marrow or peripheral blood
155 sample
- 156 • Samples must suffice quality attributes control which are denoted in (4.)
- 157 • Patient's informed consent

158 4. Exclusion Criteria

159 • Sample is not fit for state-of-the-art diagnosis, fails initial quality control. For quality
160 insurance we will exclude samples with wrong anticoagulant sent. Samples with
161 damage due to meteorological reasons (freeze-thaw damage or elevated temperature)
162 will be excluded.

163 • Samples with too scarce material jeopardizing routine gold-standard diagnosis will be
164 excluded (tumor content < 20 %).

165

166 5. Location

167 SIRIUS will be conducted as monocentric trial at the MLL.

168 **IV. STATISTICAL PLAN**

169

170 To determine the statistical significance within the endpoint analysis we will assess both
171 quantitative as well as qualitative variables. Quantitative variables will be described with the
172 number of non-missing values, mean, standard deviation, median, and minimum/maximum
173 values. Qualitative variables will be expressed as a number and percentage of patients with
174 each qualitative characteristic. The missing values are not intended to be included in the
175 calculation of percentages. Sensitivity and specificity will be assessed specific to each method,
176 with respect to internal gold standard diagnostic work-up.

177

178 **V. RISKS AND BENEFITS**

179 *Potential Direct Benefits to Subject*

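### Replaceability and routine reliability are to be concluded from diagnostically unclear cases only; the conclusions should be limited to such cases

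*Protocol*

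**What the plan says.** Section I.1 says of the current diagnostic methods: "This leads to a treatment enabling diagnosis in the vast majority of cases. However", it continues, "approximately 10 % of cases remain unresolved from a diagnostic point of view and hence do" not reach a satisfactory WHO diagnosis.

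Section I.2 asks whether WTS and/or WGS can surpass classical methods in diagnostic "precision and routine reliability. Here we will test this hypothesis in a prospective real-world" "setting under diagnostically difficult circumstances". The aim and its setting thus stand in consecutive sentences.

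Section II.1 reads "SIRIUS is conducted as a monocentric prospective case-control study. The study population" and goes on to describe patients for whom current methods did not suffice. Section II.2 sets the number at 110, all with an inconclusive diagnosis, chosen by the referring center and the principal investigator before material reaches MLL.

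Section II.4 runs three work-ups on these unclear cases: (1) at the referring site, (2) the standard MLL work-up, and (3) WGS and WTS with matching to the reference collection. Arms (2) and (3) are then compared to assess "replaceability of current gold-standard methods to either WGS or WTS and WGS/WTS" combined.

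Section III.3 requires an unsatisfactory current work-up and "Material with a minimum of 20% tumor content in bone-marrow or peripheral blood".

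On the reference data, section I.2 states: "To this end we generated a reference collection of 5,500 samples with the full spectrum of" hematological malignancies. It adds that these cases have unambiguous gold-standard diagnoses, and that both assays are available in 93% of them.

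**The concern.** To replace the current methods, WGS/WTS must do two things: help where those methods fall short, and give the right answer where they already work. The enrolled patients inform mainly the first. They are selected for an unclear or unsatisfactory work-up and for enough tumor content. The study is labelled case-control, but no clearly diagnosed group is described. The 5,500 reference cases enter only as the library for matching; no endpoint tests WGS/WTS on them.

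A good result would support WGS/WTS as an addition when the usual work-up leaves doubt. Read under the words replaceability and routine reliability, the same result could be taken as support for dropping classical methods in general. Diagnoses lost that way would fall in a part of the case mix that the trial does not sample. Selecting patients because standard work-up was unsatisfactory also tilts the comparison against standard methods.

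**Working it through.** **The plan's own figure.** The 110 comes without a derivation in the protocol, so there is nothing to reproduce. The point does not depend on it.

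**Inputs**
- *w*, the share of all cases that current methods leave unresolved: about 0.10 (section I.1). Values of 0.05 and 0.20 are used as a range.
- *g*, the net gain of arm (3) over arm (2) within that share: not in the protocol. Assumed 0.40 for illustration, with 0.30 and 0.50 as alternatives.
- *L*, the net loss of arm (3) against arm (2) among cases that current methods resolve: not in the protocol, and not observed for clearly diagnosed patients.

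**Break-even loss.** Across all cases, the net benefit of replacement is *w·g* − (1 − *w*)·*L*. It is zero when *L* = *w·g* / (1 − *w*).

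| *w* | *g* | *w·g* | Break-even *L* |
|---|---|---|---|
| 0.10 | 0.40 | 0.040 | 0.040 / 0.90 = 4.4% |
| 0.10 | 0.30 | 0.030 | 0.030 / 0.90 = 3.3% |
| 0.10 | 0.50 | 0.050 | 0.050 / 0.90 = 5.6% |
| 0.05 | 0.40 | 0.020 | 0.020 / 0.95 = 2.1% |
| 0.20 | 0.40 | 0.080 | 0.080 / 0.80 = 10.0% |

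In the first row, the gain is 4 cases per 100, and losing 4 of the other 90 undoes it.

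**Would more patients help?** Suppose arm (3) resolves 77 of 110, or 70%. The exact 95% interval is 60.5% to 78.4%, which is informative about unclear cases. If those cases stood for the unresolved 10%, the rate over all cases would be 0.10 × 0.70 + 0.90·*x*, with *x* the unobserved rate in the rest. That runs from 7% (*x* = 0) to 97% (*x* = 1). The width of 90 points does not shrink with sample size. These are logical bounds only, not plausible forecasts.

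**What the weights do not describe.** Section III.3 also lists unusual course, relapsed/refractory or non-responder status, parallel conditions, and secondary neoplasms. The tumor-content minimum narrows the sample further. The 110 are therefore not a sample of exactly that 10%, and the table illustrates the mechanism; it does not estimate the trial's result.

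**The case against.** The strongest reply is that the protocol already sets its scope. Section I.2 places the test in difficult circumstances directly after naming routine reliability, section II.4 speaks of unclear cases, and nowhere does II.4 claim replaceability for all routine practice. This largely stands: studying unclear cases is legitimate, and how often they can be resolved is answerable here. But describing the setting does not limit the conclusion, and the two broad terms are never tied back to the enrolled population. The statistical analysis plan, which is not shown, could not supply patients who are not enrolled.

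A second reply concerns which arm was inconclusive. Patients are chosen before material reaches MLL, and section III.3 can be read as referring to the referring site's work-up, while section II.2 speaks of gold-standard techniques. On the first reading, arm (2) may resolve some of the 110. Those cases would show whether arm (3) reproduces a working gold-standard answer. This also stands.

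For these reasons, three stronger readings that a reader might infer are not supported:
- That the trial says nothing about diagnoses lost without classical methods. Any case that (2) resolves and (3) misses is direct, if limited, evidence.
- That no enrolled patient has a settled diagnosis. The wider inclusion list, and a work-up that may be unsatisfactory because of clinical behavior, leave this open.
- That the cohort stands for 10 of every 100 routine cases. The inclusion list does not establish that.

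Finally, the reference collection does not fill the gap fully. Its cases are valued for unambiguous diagnoses, so they need not reflect the routine case mix, and leave-one-out matching tests the matching step and not the whole prospective pathway. That stands, and it limits what the optional part of the fix can claim.

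**Conclusion.** The point holds as a mismatch between the stated conclusions and the enrolled population, not as a fault in studying unclear cases. The trial can estimate how often WGS/WTS resolves such cases with at least 20% tumor content. It can also give limited evidence on reproducing arm (2) wherever arm (2) reaches a diagnosis. It cannot establish performance in the large majority that current methods already resolve, and so cannot support replaceability or routine reliability without restriction.

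On size: with the protocol's 10% and an assumed net gain of 40%, a loss of 4.4% among the remaining cases cancels the gain. With the same gain, the figure is 2.1% at an unresolved share of 5% and 10.0% at 20%. These figures rest on the assumed gain and on treating the unclear cases as the unresolved share. The conclusion about scope rests on neither.

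**What to change.** 1. In sections I.2 and II.4, limit the conclusions on replaceability and reliability to diagnostically unclear cases with at least 20% tumor content.
2. In section II.4, report agreement between arms (2) and (3) separately for cases that (2) resolves and cases that it does not.
3. Only if a wider replaceability aim is kept: run leave-one-out matching in the 5,500-case reference collection, removing all samples of the index patient each time. Report agreement by disease group and by assay availability, since both assays exist in only 93%. Label it as optimistic internal validation in unambiguous cases, not as proof of routine replaceability.

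Steps 1 and 2 change wording and tabulation only; no patients or assays are added. Step 3 adds computation on data the sponsor already holds. The price is a narrower headline claim.

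### II.4 adds gold-standard data to discordant WGS/WTS results inside the primary endpoint without saying which WGS/WTS result is scored

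*Protocol*

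**What the plan says.** Protocol II.4 introduces its three algorithms with "The primary endpoint will be assessed as follows: unclear cases will be" put through each of them. Algorithm (2) is the laboratory's routine gold-standard work-up. Algorithm (3) is "WGS and WTS sequencing plus matching to nearest digital sibling in 5,5k cohort"; nothing from (2) is part of that definition.

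After a first comparison of (2) and (3) with the referring site's diagnosis (1), II.4 continues: "Next results from (2) and (3) will be compared against each other to obtain an assessment of" "replaceability of current gold-standard methods to either WGS or WTS and WGS/WTS" combined. The next sentence gives the rework rule: "If both approaches do not yield a similar conclusion, specific data from (2) will be" "added to results in (3) until a definitive assessment can be made".

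Section IV plans sensitivity and specificity method by method, with the internal gold-standard work-up as reference. That is most naturally algorithm (2), although Section IV does not use the number.

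On sample size, II.2 says "SIRIUS will be conducted for a total number of 110 patients with inconclusive diagnosis by" gold-standard techniques. III.5 says "SIRIUS will be conducted as monocentric trial at the MLL".

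**The concern.** The rework has three features that matter for a diagnostic comparison. Discordance with the comparator triggers it, so concordant cases are never reopened. Data flow one way, from (2) into (3). It has no stated limit, and neither the trigger (a similar conclusion) nor the stopping point is defined.

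This is discrepant resolution. If the reworked (3) result is scored against (2), the index test contains part of its own reference, which is incorporation bias. It also fails to answer the question: replaceability asks what (3) can do without (2), whereas a result that needed data from (2) describes a combined strategy.

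At stake is the main (2)-versus-(3) comparison. As II.4 stands, the same cases can support two different figures, before and after rework, and the protocol does not say which one it will report as replaceability.

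**Working it through.** **1. What is fixed and what is open**

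- Fixed (II.4): (3) is defined without data from (2); (2) and (3) are compared for replaceability; discordant cases then have data from (2) added to (3).
- Open: whether replaceability uses (3) before or after that step, and whether sensitivity and specificity in Section IV do.
- Section VI says that data management documents will describe analysis methods. It does not say that they settle this point.

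**2. Direction**

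Let n be the cases with a conclusion from (2), x the unaided agreements, and k the discordant cases that move to the conclusion of (2) after rework.

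- Unaided agreement = x/n
- Augmented agreement = (x + k)/n, with k between 0 and n − x

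Cases that resolve towards (3), or stay discordant, add nothing. Concordant cases are not reopened, so no term reduces x. Hence augmented agreement is at least the unaided agreement, provided (2) is not revised. The same holds for sensitivity and specificity within each stratum, if a correct result there means a similar conclusion to (2).

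**3. Size, as illustration only**

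The protocol gives no expected agreement, no conversion rate and no agreement target, so there is no figure of its own to reproduce. The only documented input is 110 cases. All values of x below, and n = 80 and n = 55, are assumptions. The smaller n are shown because patients enter with an inconclusive gold-standard diagnosis, so not all may have a conclusion from (2).

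Points added per case that moves = 100/n: 100/110 = 0.91, 100/80 = 1.25, 100/55 = 1.82.

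As a rough scale, the table gives the smallest k for which (x + k)/n exceeds the upper exact (Clopper-Pearson) 95% limit of x/n. That limit is the 0.975 quantile of Beta(x + 1, n − x).

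| n | Unaided x (assumed) | Exact 95% CI, % | Discordant | Smallest k | Augmented agreement |
|---|---|---|---|---|---|
| 110 | 66 (60%) | 50.2 to 69.2 | 44 | 11 | 77/110 = 70.0% |
| 110 | 77 (70%) | 60.5 to 78.4 | 33 | 10 | 87/110 = 79.1% |
| 110 | 88 (80%) | 71.3 to 87.0 | 22 | 8 | 96/110 = 87.3% |
| 110 | 99 (90%) | 82.8 to 94.9 | 11 | 6 | 105/110 = 95.5% |
| 80 | 48 (60%) | 48.4 to 70.8 | 32 | 9 | 57/80 = 71.25% |
| 80 | 64 (80%) | 69.6 to 88.1 | 16 | 7 | 71/80 = 88.75% |
| 55 | 33 (60%) | 45.9 to 73.0 | 22 | 8 | 41/55 = 74.5% |
| 55 | 44 (80%) | 67.0 to 89.6 | 11 | 6 | 50/55 = 90.9% |

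The two figures come from the same patients, so this comparison is not a test of the change. It only shows how few reworked cases would produce a shift as large as the sampling uncertainty.

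For accuracy, assume 80 positive and 30 negative cases by (2), with unaided sensitivity 60/80 = 75.0% and specificity 24/30 = 80.0%. If half of the errors move to (2), these become 70/80 = 87.5% and 27/30 = 90.0%.

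**The case against.** The strongest reply is that II.4 is sequential. Discordance can be seen only once unaided conclusions exist and have been compared; the replaceability sentence ends before the rework sentence begins; and the rework is tied to reaching a final diagnosis for the case. Resolving unclear cases is a stated aim of the protocol's opening summary. Section IV's method-by-method accuracy also fits unaided scoring better, because a result containing data from (2) no longer belongs to method (3) alone. This reading is available. It stands as far as it goes, and for that reason a reader may not infer that the augmented result will be used: the protocol does not say so.

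Three other stronger readings also go too far.

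- A reader might infer that every error of (3) against (2) is reworked. The trigger is the lack of a similar conclusion, which is undefined, so a near-miss could escape rework and still be scored as an error.
- A reader might infer that running both work-ups in one laboratory means that (3) is contaminated. It shows only that the order of reads needs documenting.
- A reader might take the table as an estimate of bias. It rests wholly on assumed rates.

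It can also be said that agreement with (2) is not the only measure, since II.4 also compares with (1) and uses clinical follow-up, and I.2 aims to surpass classical methods. That limits the reach of the point to replaceability and to Section IV's accuracy figures.

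Finally, an SAP may settle which result is scored. But the rework rule is written into the protocol's primary endpoint, and it alters the (3) result in the paragraph that assesses replaceability. This is therefore a rule the document fixes badly, and not a detail it merely leaves for later.

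**Conclusion.** The point holds in this form: II.4 places a one-sided rework of discordant cases inside the primary-endpoint procedure and does not say which (3) result counts. If the augmented result is counted and (2) stays fixed, agreement with (2) can only stay the same or rise, and the result no longer bears on whether (2) can be replaced.

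The direction follows from the rule and needs no outside figure. The size is not computable from the protocol. It is zero if the unaided result is scored, or if every discordant case resolves towards (3) or stays discordant. Otherwise it is 0.9 points per case that moves to (2) with 110 scored cases, and more per case if fewer have a conclusion from (2).

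This should be settled before the first comparison of (2) and (3), because an unaided conclusion that was not recorded in time may not be recoverable.

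**What to change.** Add to II.4:

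> The WGS-only, WTS-only and WGS+WTS conclusions are each recorded and date-stamped before any data from (2) are added to that case. Replaceability, sensitivity and specificity are assessed on these unaided conclusions, and discordant cases count as discordant. The result after adding data from (2) is reported separately as discordance resolution (a combined strategy), with the number of cases that needed it, the tests added, and the direction of resolution.

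This keeps the case-resolution aim and makes it more informative, since it shows which conventional tests were still needed and how often. The cost is a few sentences and a dated record per case; no assay or patient is added, and the secondary endpoints in II.5 are untouched. The downside is that the headline agreement may be less favourable, and the laboratory running both work-ups must document the order of reads.

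### Does the actionable-target endpoint mislead because it counts only what WGS/WTS adds and not what it misses?

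*Protocol*

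**What the plan says.** Section II.4 of the protocol sends each unclear case through three algorithms: (1) the referring site's own diagnosis, (2) the MLL gold-standard work-up and (3) "WGS and WTS sequencing plus matching to nearest digital sibling in 5,5k cohort". Algorithm (2) includes molecular testing and "NGS based Targeted panel sequencing", so it can find targets itself.

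The secondary endpoint in Section II.5 reads "Identify number of potential actionable targets for which a therapy has been approved", followed by the restriction "but identification was missed in (1) and (2".

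Three other statements bear on the point:

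- Section II.4, on whether gold-standard methods can be replaced: "Next results from (2) and (3) will be compared against each other to obtain an assessment of".
- Section II.4, on disagreement: "If both approaches do not yield a similar conclusion, specific data from (2) will be" added to (3) until the case can be settled.
- Section IV: sensitivity and specificity are assessed for each method, "with respect to internal gold standard diagnostic work-up". It also gives the general summary rule: "Qualitative variables will be expressed as a number and percentage of patients with" each characteristic.

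**The concern.** A count restricted to what the other algorithms missed can only be zero or positive. It takes the same value whether (3) misses none of the targets found by (2) or many of them. On its own it gives gross gain, never net yield.

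That matters because the study also asks whether WGS/WTS can stand in for current methods. If the molecular tests and panel in (2) were dropped on the strength of a gain count alone, approved-therapy targets that only they detect would be lost without appearing in that count.

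The rule for disagreements seems to add to the risk. If data from (2) are merged into (3) before targets are tabulated, a target found only by (2) could be credited to (3).

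**Working it through.** The protocol gives no target rate, discordance rate, error level or power for this endpoint, so there is no planned figure to reproduce. The check is what each statement can and cannot show.

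**1. What the endpoint counts.** With three algorithms, a target found at least once has one of 2^3 − 1 = 7 detection patterns, written (1)-(2)-(3).

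- Missed in both (1) and (2): pattern 0-0-1, one cell.
- Found by (2), missed by (3): patterns 0-1-0 and 1-1-0, two cells.

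So the endpoint does not name the loss cells. However, one of seven counts logical patterns, not targets or patients, and is no measure of size. It also assumes that the misses in (1) and (2) are joint, which is the likelier reading. If they are listed separately for each algorithm, a target with pattern 0-1-1 enters the list for (1) and one with 1-0-1 enters the list for (2).

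**2. Whether another part of the plan looks the other way.** For any finding that (2) and (3) can each detect, let

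- a = found by both,
- b = found by (3) only,
- c = found by (2) only,
- d = found by neither.

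The Section II.5 count is b, further limited to targets that (1) also missed. Section II.4 compares (2) and (3) with each other, so b and c are both within its scope. Taking the reference in Section IV to be algorithm (2):

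- sensitivity of (3) = a / (a + c), so 1 − sensitivity = c / (a + c);
- specificity of (3) = d / (b + d), so 1 − specificity = b / (b + d).

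The quantity said to be missing, c, is what sensitivity against (2) measures. Neither section repeats the word targets. But (2) includes molecular testing and a panel, so its results can naturally include molecular findings.

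**3. Whether merging hides losses.** Data from (2) are added to (3) only when the two approaches fail to reach a similar conclusion. That condition cannot be judged unless a result of (3) alone exists and has already been compared with (2). The step also shows which data from (2) were needed.

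**4. Whether the count is used to support replacement.** Section II.4 assigns replacement to the (2)-versus-(3) comparison. Section II.5 lists the target count as a separate secondary item. No statement carries the count over into the replacement question.

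**5. What an extra table would give.** If all 110 planned patients had both results, exact (Clopper-Pearson) 95% intervals for the proportion with a lost target would be, for example:

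- 0/110: 0% to 1 − 0.025^(1/110) = 0.0330, that is 3.3%;
- 5/110 = 4.5%: 1.5% to 10.3%.

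The counts 0 and 5 are illustrations, not predictions. The intervals describe the precision of an additional table and do not measure an error in the plan.

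**The case for a change.** The strongest contrary argument is that the direction is fixed in the endpoint's own wording and is not a detail left open. The comparison in Section II.4 concerns results and a similar conclusion. Two approaches can agree on the diagnosis while one of them misses a target, so diagnostic agreement does not guarantee that a lost target is seen. Section IV does not tie sensitivity to targets either. Counting both directions would need only a little extra tabulation from results already planned for every case.

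Part of this stands. No statement expressly tabulates targets found by (2) and missed by (3), and a reader who wants net target yield will not find it named. Recording the result of (3) before anything from (2) is added is also good practice.

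It does not make the endpoint wrong. The proposal would leave the existing count untouched and add a cross-tabulation, intervals and counting rules. A SAP commonly supplies these, and only the protocol was available here. Section VI also says that the data management documents will set out analysis methods. To say that readers will not learn of losses is to predict a report nobody has seen, and Sections II.4 and IV, in their general terms, point the other way.

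**Conclusion.** The concern does not hold. Section II.5 defines a coherent added-yield count, suited to patients in whom standard work-up gave no clear diagnosis. Followed as written, it answers the question it poses. The reverse direction is covered in general terms by the mutual comparison of (2) and (3) and by sensitivity against the gold-standard work-up, and the merging rule presupposes that (3) has first been compared on its own.

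No size of effect can be attached, because the documents give no values for either kind of discordance. The conclusion rests on three assumptions: the gold-standard reference in Section IV is algorithm (2); results in Section II.4 include molecular findings as well as the final diagnosis; and the target count is not later presented as evidence for replacement. If it were, the number of targets found only by (2) would have to stand beside it. Naming both directions is an optional refinement, not the correction of an error.
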